11.2 Subject demographics and other baseline characteristics

Summary statistics will be provided for demographic and baseline characteristics by treatment group and overall. Baseline characteristics will be presented for both the study and fellow eye. Number and percentage will be presented for categorical variables and descriptive statistics, including mean, standard deviation, quartiles, minimum and maximum will be presented for continuous variables.

Relevant medical history, current medical conditions, results of laboratory screens, drug tests and any other relevant information will be summarized by treatment group. Ocular parameters will be presented separately for study and fellow eye.

11.3 Treatments (study drug, rescue medication, other concomitant therapies, compliance)

Data for study drug administration, concomitant therapies, and compliance will be summarized by treatment group with separate presentation for study and fellow eye.

11.4 Analysis of the primary variable(s)

The primary objective aim of this study is to evaluate, in the study eye, the efficacy of 12 (every 28 days) IVT injections of CLG561 as a monotherapy and in combination with LFG316 as compared to sham on the growth of GA lesion as assessed by FAF.

11.4.1 Variable(s)

The primary endpoint of this study is the change in geographic atrophy lesion size [mm^2] in the study eye between Day 337 and Baseline as measured by FAF.

11.4.2 Statistical model, hypothesis, and method of analysis

The primary efficacy hypotheses are that the change in geographic atrophy lesion size in the study eye under CLG561 as a monotherapy and/or in combination with LFG316 is lower than the sham arm. The null and alternative hypotheses are:

$$H_{01}: \mu_{CLG} - \mu_{Sham} \geq 0 \text{ mm}^2 \text{ vs } H_{A1}: \mu_{CLG} - \mu_{Sham} < 0 \text{ mm}^2$$

$$H_{02}: \mu_{CLG+LFG} - \mu_{Sham} \geq 0 \text{ mm}^2 \text{ vs } H_{A2}: \mu_{CLG+LFG} - \mu_{Sham} < 0 \text{ mm}^2$$

μ_{CLG} , $\mu_{CLG+LFG}$ and μ_{Sham} being the corresponding unknown true treatment specific mean changes from Baseline to Day 337.

Novartis

Confidential

Page 82

Amended Protocol Version No. 01 (Clean)

Protocol No. CCLG561X2201A

The comparison of the two active arms will be done descriptively.

Corporate Confidential Information

The lesion size change from baseline to Day 337 will be analyzed by an analysis of variance model including, but not limited to, the class variables representing categories of baseline lesion size (edge length) and categories of lesion location.

The primary efficacy analysis set will be the PP set.

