Data analysis	
Primary Endpoint Change in GA lesion size from baseline to Day 337
 
Hypotheses One-sided hypotheses of superiority of active related to the comparison of each of the two active arms vs control (sham injections). The comparison of the two active arms will be done descriptively.
 
Primary analysis data set The primary efficacy analysis data set is a per-protocol (PP) set. Key PP criteria are compliance with the GA specific inclusion criteria, the monthly injection schedule up to Day 337 (not missing greater than 1 in any 6 months period or not missing 2 consecutive doses) and available baseline and Day 337 and/or Day 253 lesion size assessments. Missing values of lesion size on Day 337 will be imputed based on linear regression/extrapolation.
 
Statistical testing strategy For hypotheses-testing a global one-sided alpha of 0.2 is considered. With the two hypotheses being tested in parallel using the Bonferroni multiplicity adjustment, the nominal one-sided alpha for each single hypothesis will be 0.1.
 
Statistical method The lesion size change from baseline to Day 337 will be analyzed by an ANOVA model including but not limited to the class variable representing categories of baseline lesion size (edge length) and categories of lesion location.
 
Sample size A sample size of 30 per-protocol (PP) evaluable subjects per treatment arm will allow identification of a treatment difference of 0.67 mm² in lesion size change from baseline to Day 337 (representing a 33% reduction in lesion growth rate, assuming an average natural disease progression of 2.0 mm² per year) at a one-sided alpha level of 0.1 with a power of 80% assuming a standard deviation of 1.2 mm². In anticipation of a drop-out /protocol deviation rate of 20%, a total sample size of ~114 randomized subjects (~38 subjects/arm) is planned for the current study to ensure sufficient study completers for the above described PP analysis. Depending on ongoing monitoring of the drop-out/protocol deviation rate the need for additional recruitment will be assessed to ensure 90 PP evaluable subjects are available for the Day 337 analysis.

Key words	Geographic atrophy, GA, macular degeneration, dry AMD, IVT, intravitreal, retinal diseases, FAF

1 Introduction

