11.4.4 Supportive analyses

The primary efficacy analysis will be performed using the PP set with treatment as randomized. Sensitivity analysis regarding major protocol deviations will be performed on the primary efficacy endpoint using the full analysis set as randomized. In case of deviations from the treatment allocation as randomized the full analysis set will also be analyzed on an as 'as treated' basis.

An additional sensitivity analysis will be performed assuming linear lesion growth in the study for all treatment for the one year observation period using a Mixed-Effect Model Repeated Measure (MMRM) model with random slopes and including class-variables as specified for the primary analysis.

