11.5 Analysis of secondary and exploratory variables

11.5.1 Efficacy endpoints

Analyses will be performed for both the PP set and the FAS.

Potential treatment effects will primarily be assessed based on the difference in change from baseline in the study eye between active treatment and sham treatment. In addition, the corresponding difference between study and fellow eye will be explored within the active treatment arms.

At time points assessed, each efficacy endpoint will be presented graphically and by descriptive statistics provided for observed absolute values and changes from baseline. Changes from baseline will be compared between treatment arms using ANOVA models and/or stratified/unstratified Cochran-Mantel-Haenszel Tests.

Corporate Confidential Information

For treatment differences and differences between study and fellow eye 80% confidence intervals will be provided.

The following secondary endpoints will be evaluated:

- Change in geographic atrophy lesion size from baseline to Days 85, 169, 253, 337 and 421 as measured by fundus auto-fluorescence
- Change in BCVA, low luminance visual acuity and low luminance visual acuity deficit from baseline by visit up to Day 337 as measured by ETDRS in the overall population and in subsets of patients with baseline visual acuity < 73 letters
- Subject status regarding ≥ 15 letters, ≥ 10 letters, and ≥ 5 letters change from baseline in BCVA by visit up to Day 337
- Average change in BCVA/low luminance visual acuity/low luminance visual acuity deficit from baseline to the period Day 281 to Day 337

For the changes in geographic atrophy lesion size from baseline between either of the active arms and sham as measured by FAF, the same analysis model used for the primary hypothesis (Section 11.4.2) will be used.

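### The one form named for baseline lesion size in the primary ANOVA is categories of edge length; committing to a continuous term would gain a little precision at almost no cost

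*Protocol*

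**What the plan says.** Section 11.4.2 describes the primary model as an "analysis of variance model including, but not limited to, the class variables" that follow, and these are "class variables representing categories of baseline lesion size (edge length) and categories of lesion location". The Data analysis row of the synopsis agrees: "ANOVA model including but not limited to the class variable representing categories of baseline lesion size". Both statements leave the list of terms open. Neither gives the number of categories or the cut-points, and text has been withheld just before the model sentence in Section 11.4.2.

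The same form carries over to other analyses. The random-slopes sensitivity model in Section 11.4.4 is fitted "including class-variables as specified for the primary analysis". Section 11.5.1 analyses the secondary lesion-size changes with "the same analysis model used for the primary hypothesis".

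For the other efficacy endpoints, including best-corrected and low-luminance acuity, Section 11.5.1 says: "Changes from baseline will be compared between treatment arms using ANOVA models and/or stratified/unstratified Cochran-Mantel-Haenszel Tests". No baseline covariate is named there, and withheld text follows directly.

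**The concern.** Edge length is a continuous measurement, and the endpoint is untransformed area change in mm² (Section 11.4.1). If a lesion border advances at a steady rate, a larger lesion gains more area per year, roughly in proportion to its edge length. Eligible areas run from 3 to 16 mm² (Section 4.1), so edge length runs from √3 = 1.7 mm to √16 = 4.0 mm, more than a twofold range. The plan itself treats edge length as relevant to outcome, since it is named in the model and again as a subgroup factor in Section 11.4.5.

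Cutting such a variable into categories leaves the variation within each category in the residual. At stake is the precision of the two active-versus-sham comparisons and of every lesion-size analysis that reuses the model. The data needed for a continuous term are already collected.

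**Working it through.** **1. The plan's own sample size.** Inputs from Section 11.6: difference 0.67 mm², SD 1.2 mm², one-sided alpha 0.1, power 80%, 30 evaluable per arm, 20% loss.

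- n per arm = 2 × [1.2 × (1.2816 + 0.8416) / 0.67]² = 28.9, so 29 against 30 stated.
- Power at 30 per arm = Φ(0.67 / (1.2 × √(2/30)) − 1.2816) = 81.1%.
- 30 / 0.8 = 37.5, so 38 per arm and 114 in total, as stated.

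The stated size reproduces. It uses the unadjusted SD and takes no credit for any covariate.

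**2. How much edge length could explain.** The documents give no correlation between baseline size and growth, so a growth model has to be assumed. With edge length E advancing by k per year, area growth = (E + k)² − E² = 2kE + k². Assume areas uniform on 3 to 16 mm² and k normal and independent of E, tuned to the plan's mean of 2.0 and SD of 1.2 mm². This gives k with mean 0.311 and SD 0.167.

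- Mean of E = (2/3)(16^1.5 − 3^1.5)/13 = 3.016; variance of E = 9.5 − 3.016² = 0.406.
- Mean growth = 2 × 0.311 × 3.016 + 0.311² + 0.167² = 2.00, as intended.
- Share of variance explained by continuous E = (2 × 0.311)² × 0.406 / 1.2² = 0.109, a correlation of about 0.33.

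**3. What categories keep.** For two categories split at the median area of 9.5 mm², the mean edge lengths are 2.470 and 3.561. The between-category variance is (1.091/2)² = 0.297, which is 73% of 0.406, so the explained share is 0.109 × 0.73 = 0.080. Simulation gives 0.080, 0.096 and 0.101 for two, three and four equal-sized categories.

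Excess residual variance over continuous = (1 − R²cat)/(1 − R²cont) − 1. Power uses residual SD = 1.2 × √(1 − R²) in the formula of step 1.

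| Baseline term | R² | Excess variance | Power at 30 per arm |
|---|---|---|---|
| Two categories | 0.080 | 3.3% | 83.5% |
| Three categories | 0.096 | 1.5% | 84.0% |
| Four categories | 0.101 | 0.8% | 84.1% |
| Continuous | 0.109 | reference | 84.4% |

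The largest gain is 0.9 percentage points, or about 3 of 90 subjects (0.033 × 90).

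**4. Sensitivity to the assumed correlation r.** With a normal covariate, two categories keep 64% of r² and three keep 79%. Power at 30 per arm from two categories to continuous is:

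- r = 0.1: 81.3% to 81.4%
- r = 0.2: 81.8% to 82.3%
- r = 0.3: 82.8% to 83.8%
- r = 0.5: 85.9% to 88.8%

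A gain of two to three points needs a correlation well above the 0.33 that constant edge growth implies.

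**5. Acuity, only if no baseline term is used.** With equal variances at baseline and follow-up, adjusted variance over change-score variance = (1 + r)/2, where r is now the baseline–follow-up correlation. For assumed r of 0.9 and 0.6 this is 0.95 and 0.80, a reduction of 5% to 20%. The protocol gives no value for r.

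**The case against.** **The model is not closed.** A reader might infer that baseline size can enter only as categories. The text does not say so, because Section 11.4.2 and the synopsis both leave the term list open and a continuous term is compatible with them. That stands, and it limits the point to the form named. Permission is still not commitment, and since Section 3.2 leaves the sponsor unmasked, a useful covariate is better fixed in advance.

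**Categories are defensible.** They need no linearity assumption and match the subgroup factors in Section 11.4.5. Section 4 also mentions stratification factors, without naming them. This stands as a reason to keep any stratification categories, not as a reason to omit a continuous term. The calculation above makes growth linear in edge length by construction, which favours the continuous term.

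**The effect is small.** This is correct. A reader might suspect a power shortfall, but the sample size reproduces without any covariate credit.

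**Acuity.** A reader might infer that the acuity analyses discard baseline information. The documents do not establish that: withheld text follows the sentence, stratified tests are also allowed, and the SAP, which commonly holds such detail, is not shown. Nor does choosing the worse-seeing eye when both qualify (Section 4) bias the comparison, because the rule applies equally in every randomized arm.

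**Conclusion.** The point holds as a minor efficiency matter for the lesion-size analyses. The only form named for baseline lesion size is categorical, and it runs through the primary, sensitivity and secondary lesion-size models. Under roughly linear growth with edge length, the cost is about 1% to 3% extra residual variance (four down to two categories) and less than one percentage point of power at 30 per arm. The figures rest on constant edge growth, an assumed spread of baseline areas and an unstated number of categories. Even a continuous term removes chance baseline imbalance completely only if the relation is linear. Type I error and the validity of the comparison are not in question. The acuity part is a conditional suggestion, not a demonstrated fault.

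**What to change.** In Section 11.4.2 and the synopsis, pre-specify continuous baseline edge length (square root of baseline area) as a covariate in the primary model. Keep lesion location as a class variable, along with any categories used for stratification. Carry the same covariate into the Section 11.4.4 sensitivity model and the lesion-size models of Section 11.5.1.

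Where acuity changes are compared by ANOVA, include the continuous baseline of the same measure, unless the withheld text or the SAP already does so.

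The change is to wording only and needs no new data or subjects. Its price is one degree of freedom and an assumed linear relation, which a plot or a quadratic term can check.

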11.4.3 Handling of missing values/censoring/discontinuations

In the primary efficacy analysis which is based on the PP set, a subject will have in the study a baseline lesion size assessment and a corresponding assessment on Day 337 and/or Day 253. For subjects with missing values of lesion size in the study eye on Day 337, the missing value will be imputed based on linear regression/extrapolation (which at minimum will be based on the Day 253 assessment).

11.4.4 Supportive analyses

The primary efficacy analysis will be performed using the PP set with treatment as randomized. Sensitivity analysis regarding major protocol deviations will be performed on the primary efficacy endpoint using the full analysis set as randomized. In case of deviations from the treatment allocation as randomized the full analysis set will also be analyzed on an as 'as treated' basis.

An additional sensitivity analysis will be performed assuming linear lesion growth in the study for all treatment for the one year observation period using a Mixed-Effect Model Repeated Measure (MMRM) model with random slopes and including class-variables as specified for the primary analysis.

11.4.5 Subgroup analyses

The following subgroups will be analyzed for the primary efficacy endpoint using the same approach:

- Age category (< 75 years and \geq 75 years)
- Gender (male and female)
- Baseline BCVA categories (<60 letters, 60 – 73 letters, and $>$ 73 letters)
- Baseline lesion size (edge-length)
- Baseline lesion location
- Baseline lesion type: uni-focal vs multi-focal
- Corporate Confidential Information

11.5 Analysis of secondary and exploratory variables

11.5.1 Efficacy endpoints

Analyses will be performed for both the PP set and the FAS.

Potential treatment effects will primarily be assessed based on the difference in change from baseline in the study eye between active treatment and sham treatment. In addition, the corresponding difference between study and fellow eye will be explored within the active treatment arms.

At time points assessed, each efficacy endpoint will be presented graphically and by descriptive statistics provided for observed absolute values and changes from baseline. Changes from baseline will be compared between treatment arms using ANOVA models and/or stratified/unstratified Cochran-Mantel-Haenszel Tests.

Corporate Confidential Information

For treatment differences and differences between study and fellow eye 80% confidence intervals will be provided.

The following secondary endpoints will be evaluated:

- Change in geographic atrophy lesion size from baseline to Days 85, 169, 253, 337 and 421 as measured by fundus auto-fluorescence
- Change in BCVA, low luminance visual acuity and low luminance visual acuity deficit from baseline by visit up to Day 337 as measured by ETDRS in the overall population and in subsets of patients with baseline visual acuity < 73 letters
- Subject status regarding ≥ 15 letters, ≥ 10 letters, and ≥ 5 letters change from baseline in BCVA by visit up to Day 337
- Average change in BCVA/low luminance visual acuity/low luminance visual acuity deficit from baseline to the period Day 281 to Day 337

For the changes in geographic atrophy lesion size from baseline between either of the active arms and sham as measured by FAF, the same analysis model used for the primary hypothesis (Section 11.4.2) will be used.

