--	---

Novartis

Confidential

Page 23

Amended Protocol Version No. 01 (Clean)

Protocol No. CCLG561X2201A

Investigational and reference therapy	
Investigational Products/Treatments:
 
CLG561 (anti-properdin Fab)
 
 • IVT Injection • 10 mg/100 µL • Every 28 days for total of 12 injections 
CLG561 (anti-properdin Fab) combined with LFG316 (anti-C5 IgG)
 
 • IVT Injection (co-injection) • CLG 561 5 mg/ 50 µL mixed with LFG316 5 mg/ 50 µL (total 100 µL) are mixed in a vial and will be administered as a 100 µL total volume via a single syringe • Every 28 days for total of 12 injections 
Control Products/Treatments:
 
 • Sham injections • Hub of an empty syringe (without a needle) will be placed against the eye • Every 28 days for total of 12 sham-injection procedures
Efficacy /PK/PD assessments	
 • GA lesion as measured by FAF (both eyes) • BCVA (both eyes) • Low luminance visual acuity (both eyes) • Serum concentration of total CLG561 and total LFG316 • Serum levels of anti-drug antibodies (ADA; anti-CLG561 and anti-LFG316 antibodies) 
Corporate Confidential Information

Safety assessments	
 • AEs (AEs) (incidence, severity, overall assessment) • Vital signs (blood pressure, heart rate) • Laboratory evaluations • Hematology • Chemistry including liver function tests • Urinalysis • Complete ophthalmic exam (slit lamp, dilated fundus exam, BCVA, IOP) 
Corporate Confidential Information

Other assessments	

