3.2 Rationale of study design

The design of this study will address the primary objectives of efficacy and safety of every 4 weeks IVT injection of monotherapy with CLG561 (10 mg), as well as the combination of LFG316 and CLG561 (5 mg of each) in subjects with GA. Since there is currently no product approved for the treatment of GA, no active comparator is included in the current study. The control for this study will be a sham injection, which is a common and well-established method of control for studies of IVT medications.

Subjects and certain study personnel, but not the Investigator or Sponsor, will be masked to treatment randomization. This approach was chosen for two reasons:

1. Opalescence of the IVT formulation is likely to be visible in the peripheral vitreous, particularly at early visits and would identify actively treated subjects to the study ophthalmologists
2. The primary endpoint is based on objective evaluations by a central reading facility, which will be masked to treatment assignment

Treatment randomization between the active arms and sham allows the evaluation of safety characters of CLG561 as a monotherapy and in combination with LFG316 in a balanced and objective manner. All study subjects will undergo the same study assessments and receive their assigned study treatments under the same dosing interval (every 28 days). All treatment arms will proceed in parallel to each other.

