The Investigator must ensure that all subjects being considered for the study meet the following eligibility criteria. No additional eligibility criteria must be applied by the Investigator in order to make sure that the study population is representative of all eligible subjects.

Subject selection is established by checking through all eligibility criteria at screening and confirmed at baseline. A relevant record (e.g. checklist) of the eligibility criteria must be stored with the source documentation at the study site.

Deviation from any entry criterion excludes a subject from enrollment into the study. If BOTH eyes qualify, the eye with the worse visual acuity will be selected as the study eye.

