4.1 Inclusion criteria

Subjects eligible for inclusion in this study have to fulfill all of the following criteria:

1. Able and willing to provide written informed consent and in the opinion of the Investigator, the subject is able to complete the duration of the study
Note: Informed consent must be obtained before any assessment is performed.
2. Male or female GA subjects ≥ 50 years of age
3. GA in BOTH EYES. **One eye MUST meet the following criteria** with lesion size assessed by FAF and measured by the CRC.
 - IF GA lesion is multifocal, THEN the total lesion area must be between 3-16 mm² and at least one lesion with an area of at least 1.25 mm²
 - IF GA lesion is unifocal, THEN the lesion area must be between 8-16 mm²
4. Presence of hyper-autofluorescence adjacent to at least 10% of the perimeter of GA the study eye

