7.5 Early study termination

The study may be terminated at any time for any reason by Sponsor. Should this be necessary, subjects must be seen as soon as possible and treated as a prematurely withdrawn subject. The Investigator may be informed of additional procedures as requested by the Sponsor in order to ensure that adequate consideration is given to the protection of the subject's interests.

The Investigator is responsible for informing IRBs/IECs of the early termination of the trial. In the case of representation by a central IRB, the Sponsor may be delegated this responsibility.

8 Procedures and assessments

Subjects must be seen for all visits on the designated day, with the assessments performed as per schedule, within the allowed "visit/assessment window", and as specified in the MOP.

A single rescreening is permitted only for patients who failed screening under the original protocol but who would have qualified under the amendment 1 revised selection criteria. In addition to the criteria that were changed, the rescreened patients must fulfill the unchanged selection criteria at both screenings to be eligible. Since the inclusion criterion related to lesion size is now only relevant to a single eye (study eye), for lesion size, the rescreening is limited to eyes which qualified in the original screening. For example if the left eye qualified in the original screening, only the left eye can be rescreened as the study eye. If both eyes had qualified previously on the basis of the lesion size but the eyes had failed on the basis of the visual acuity both eyes are candidates for rescreening.

The subject number previously used will be retained in the database. A new subject number is not required. The original informed consent date is retained in the database. The new informed consent date is captured in the source. A new screening date with data for the assessments is captured in the database.

All data obtained from these assessments must be supported in the subject's source documentation. Source documentation must be available for all data collected during the study. IF it becomes necessary to repeat an evaluation, THEN the results of the repeat evaluation must be recorded in the source documents and the valid measurements and evaluation must be recorded on the eCRF.

All screening, baseline and pre-injection assessments must be completed prior to drug

Novartis

Confidential

Page 59

Amended Protocol Version No. 01 (Clean)

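### The exploratory study-versus-fellow-eye difference is planned within the active arms, where eye selection alone could move it from zero; contrasting it with sham would be a cheap improvement

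*Protocol*

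**What the plan says.** Section 11.5.1 makes the randomised comparison the main basis for efficacy: treatment effects "will primarily be assessed based on the difference in change from baseline in the study eye" between active and sham. It then adds a second look, in which "the corresponding difference between study and fellow eye will be explored within the active treatment arms". On precision it states: "For treatment differences and differences between study and fellow eye 80% confidence intervals will be provided". Section 11.1 describes the fellow eye as the reference for a within-subject comparison. Part of Section 11.5.1 is redacted; the visible text plans no sham contrast of the eye difference.

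Four other places determine how alike the two eyes are and what data exist:

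- **Section 4.1.** GA is required in both eyes, but only one eye must meet the area limits (3-16 mm² if multifocal, 8-16 mm² if unifocal). The next criterion also concerns one eye: "Presence of hyper-autofluorescence adjacent to at least 10% of the perimeter of GA the study eye".
- **Section 4.** "If BOTH eyes qualify, the eye with the worse visual acuity will be selected as the study eye".
- **Section 8**, on rescreening, confirms the one-eye rule for lesion size: "Since the inclusion criterion related to lesion size is now only relevant to a single eye (study eye").
- **Synopsis and Section 3.2.** The efficacy assessments include "GA lesion as measured by FAF (both eyes"), and "All study subjects will undergo the same study assessments", so sham subjects have the same fellow-eye imaging.

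**The concern.** A study-minus-fellow difference within one arm estimates the drug effect only if, untreated, the two eyes would grow equally on average. The entry rules give no assurance of that. The study eye is chosen by lesion area, by the autofluorescence at its margin and, when both eyes qualify, by worse acuity. The fellow eye need only have GA. Any of these can produce a mean difference in growth between the eyes that has nothing to do with treatment, in either direction.

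At stake is how an exploratory interval will be read. Section 1.2 describes the study as a proof of concept, meant to show whether further development is warranted. An 80% interval that lies wholly on the favourable side invites an efficacy reading even when labelled exploratory. The sham arm went through the same eye selection before randomisation, so it measures the offset directly, but the visible method does not use it.

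**Working it through.** **Inputs from the protocol (Section 11.6).** 30 per-protocol subjects per arm, SD 1.2 mm² for the study-eye change, difference 0.67 mm², one-sided alpha 0.1.

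**Assumptions, because the documents give no value.** Fellow-eye SD s2 = 1.2 mm² (1.5 as a variation), between-eye correlation rho = 0.3, 0.5 or 0.7, and selection offset b = 0.1 or 0.2 mm² in the favourable direction.

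**Step 1: the plan's own figure.** The standard error of the study-eye active-minus-sham difference is 1.2 × √(2/30) = 0.310. The noncentrality is 0.67/0.310 = 2.16 on 58 df, which gives power 0.807 at one-sided 0.1. The stated 80% is reproduced. Allowing for 20% loss, 30/0.8 = 37.5, so 38 per arm and 114 in total.

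**Step 2: spread of the eye difference.** SD of the difference = √(s1² + s2² − 2·rho·s1·s2), with s1 = 1.2. The within-arm SE is this SD divided by √30; the half-width of the 80% interval is t(0.90, 29 df) = 1.311 times the SE.

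| s2 | rho | SD of difference | Within-arm half-width |
|---|---|---|---|
| 1.2 | 0.3 | 1.420 | 0.340 |
| 1.2 | 0.5 | 1.200 | 0.287 |
| 1.2 | 0.7 | 0.930 | 0.223 |
| 1.5 | 0.3 | 1.616 | 0.387 |
| 1.5 | 0.5 | 1.375 | 0.329 |
| 1.5 | 0.7 | 1.082 | 0.259 |

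**Step 3: chance of a wholly favourable within-arm interval with no drug effect.** This is P(T > 1.311), where T is noncentral t with 29 df and noncentrality b/SE.

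| s2 | Offset b | rho 0.3 | rho 0.5 | rho 0.7 |
|---|---|---|---|---|
| 1.2 or 1.5 | 0 | 10% | 10% | 10% |
| 1.2 | 0.1 | 18% | 20% | 24% |
| 1.2 | 0.2 | 30% | 35% | 45% |
| 1.5 | 0.1 | 17% | 19% | 22% |
| 1.5 | 0.2 | 27% | 31% | 39% |

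**Step 4: the contrast with sham.** Eye selection precedes randomisation, so b has the same expectation in every arm and drops out of active minus sham. In a simulation of 20,000 trials without drug effect (n = 30 per arm, SD 1.2, rho 0.7, favourable offset 0.2), the within-arm interval excluded zero on either side in 47% of trials against a nominal 20%. The contrast averaged zero and excluded zero in 20%.

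**Step 5: what the contrast costs.** Its SE is √2 = 1.41 times the within-arm SE. Half-widths (58 df) are 0.475, 0.402 and 0.311 at rho 0.3, 0.5 and 0.7 with s2 = 1.2, against 0.402 for the study-eye comparison. The two are equally precise when s2² = 2·rho·s1·s2, that is rho = s2/(2·s1): 0.500 with s2 = 1.2 and 0.625 with s2 = 1.5. Below that correlation the contrast is the less precise of the two. At rho 0.3 its power for 0.67 mm² is 70% (62% with s2 = 1.5), against 81% for the study-eye comparison.

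**Step 6: imperfect cancellation.** If exclusions left a residual offset of 0.1 mm² between arms (assumed), the contrast's own false-favourable rate would rise from 10% to 16-19% for rho 0.3 to 0.7 (15-18% with s2 = 1.5).

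**The case against.** The strongest reply is that nothing here is misstated. The protocol says only that the difference will be explored, as an addition, with no test, alpha or decision attached. The randomised study-eye comparison already answers the efficacy question, and the proposed contrast targets the same effect with no extra protection against bias. Model details for such an analysis normally belong in the SAP, which is not shown. Part of Section 11.5.1 is redacted, the sentence on 80% intervals names no arm, and Section 11.1 uses both eyes without exempting sham, so sham eye differences may well be presented. The eyes are also made more alike by requiring GA in both and by excluding CNV, other retinal disease and non-AMD macular atrophy in either. All of this stands and keeps the severity low. It does not remove the point that the one method stated for the eye difference cannot separate a drug effect from eye selection.

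Three stronger readings are tempting but not supported:

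- **That the contrast would rescue power.** A reader might note that an opposite offset of 0.2 mm² cuts within-arm power for 0.67 mm² from 90% to 69% at rho 0.3 (s2 = 1.2). The contrast's power there is 70%. At rho 0.5 and 0.7 the pairs are 80% and 81%, and 93% and 93%. There is no meaningful gain even in the adverse case, and with a smaller adverse offset the contrast has less power.
- **That the change is free.** No new data are needed, but precision is lost, as shown above. Cancellation is exact in expectation only as randomised. The FAS and especially the PP set apply post-randomisation conditions, and fellow-eye treatment that differs by arm could also leave a residual.
- **That fellow-eye treatment goes unreported.** Section 11.3 already summarises concomitant therapies by treatment group, separately for each eye.

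**Conclusion.** The point holds as a low-severity improvement to an exploratory analysis. On the visible text, the study-minus-fellow difference is examined within the active arms, and the entry rules allow that difference to be nonzero without a drug effect. With an assumed offset of 0.2 mm² and equal SDs, the false-favourable rate of a within-arm 80% interval is 30-45% instead of 10%; with 0.1 mm² it is 18-24%; with no offset there is no distortion. The offset, the correlation and the fellow-eye SD are assumptions, and the direction of the offset cannot be known in advance. A reader should not infer that the primary result is biased: it rests on the randomised study-eye comparison, which eye selection does not affect. Nor do the documents show that a material offset exists.

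**What to change.** In Section 11.5.1, or in the SAP before database lock:

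1. Compute the study-minus-fellow change from baseline in all three arms.
2. Report the active-minus-sham contrast of that difference, with its 80% interval, as the fellow-eye analysis.
3. Show the within-arm differences, sham included, as descriptive only.
4. Keep the randomised study-eye comparison as the main estimate.
5. State that the selection offset cancels in expectation only as randomised, so that FAS and PP results may retain a residual.

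No new visit, image or subject is needed, because FAF of both eyes is already scheduled in every arm. The cost is some programming and a wider interval.
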